### Reduction in MRM Days per Month in the OLE Phase

The number of MRM days per month in the OLE phase will be examined relative to the number of MRM days per month in the OP for menstrual migraine evaluable OL rimegepant mITT menstruating female subjects, i.e., defined as OL rimegepant mITT menstruating female subjects with  $\geq 1$  day of MR efficacy data and  $\geq 14$  days of eDiary efficacy data (not necessarily consecutive) in both the OP analysis period and at least one month (i.e., 4-week interval) in the on-OL rimegepant efficacy analysis period.

Months in the OLE phase are defined in Section 6.3.1.2.

Analyses will be based on eDiary efficacy dates in the OP and on-OL rimegepant efficacy analysis periods.

The number of MRM days per month will be prorated to 28 days and derived as follows:

- OP: See Section 6.3.1.1.
- Month (i.e., 4-week interval) in the on-OL rimegepant efficacy analysis period:  $28 \times (\text{total number of MRM days in the month}) / (\text{total number of efficacy data days in the month})$ .  
Subjects must have  $\geq 1$  day of MR efficacy data in the specified month to be evaluable.
- Overall OL rimegepant mean:  $28 \times (\text{total number of MRM days through Month 13 in the on-OL rimegepant efficacy analysis period}) / (\text{total number of efficacy data days through Month 13 in the on-OL rimegepant efficacy analysis period})$ .

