#### **6.3.1.1 Reduction in Migraine Days per Month in the DBT Phase: Primary Efficacy Endpoint**

The number of migraine days per month in the DBT phase will be examined relative to the number of migraine days per month in the OP for evaluable mITT subjects, i.e., subjects with  $\geq$

14 days of eDiary efficacy data (not necessarily consecutive) in both the OP analysis period and  $\geq 1$  month (i.e., 4-week interval) in the on-DBT analysis period.

Months in the DBT phase are defined as follows:

- Month 1 ( $\leq 4$  weeks; study days 1 to 28)
- Month 2 ( $> 4$  to  $\leq 8$  weeks; study days 29 to 56)
- Month 3 ( $> 8$  to  $\leq 12$  weeks; study days 57 to 84)

Analyses will be based on eDiary efficacy dates in the OP and on-DBT efficacy analysis periods.

The number of migraine days per month will be prorated to 28 days and derived as follows:

- OP:  $28 \times (\text{total number of migraine days in the OP analysis period}) / (\text{total number of efficacy data days in the OP analysis period})$ .
- Month (i.e., 4-week interval) in the on-DBT efficacy analysis period:  $28 \times (\text{total number of migraine days in the month}) / (\text{total number of efficacy data days in the month})$ . Subjects must have  $\geq 14$  days of efficacy data (not necessarily consecutive) in the specified month to be evaluable.
- Overall DBT mean:  $28 \times (\text{total number of migraine days through Month 3 in the on-DBT efficacy analysis period}) / (\text{total number of efficacy data days through Month 3 in the on-DBT efficacy analysis period})$ .

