### **6.3.3 Exploratory Efficacy Endpoints**

#### **6.3.3.1 Reduction in MRM Days per Month**

Female subjects will record their menstrual period start and stop dates in a menstrual period log. Menstruating females will be identified as females with either (1) a “yes” response to the question about experiencing menstrual periods on the Demographics CRF (see Section 6.2.5), or (2) at least one complete menstrual period start date from the Menstrual Period Log CRF.

An eDiary reference time point date is considered to be exclusively in a menstrual interval if the complete menstrual period start date – 2 days  $\leq$  eDiary reference time point date  $\leq$  complete menstrual period start date + 2 days.

A day of MR efficacy data is defined as a non-missing eDiary efficacy date inclusively in a menstrual interval.

An MRM day is defined as a non-missing eDiary migraine date inclusively in a menstrual interval.

MRM days per month will be assessed as “MRM days per 4 weeks” to correspond with the 4-week visit schedule. MRM days per month are based on data from the previous visit to the current visit (i.e., 4-week interval), and are prorated to account for missing migraine reports.

A by-subject listing of menstrual periods that includes efficacy analysis period will be provided for enrolled female subjects, and will display COVID-19 visit impact code for visits impacted by COVID-19 (see Section 9.1.5.2).

A by-subject listing of MRM days will be provided for menstruating female treated subjects, and will present the following: number of MRM days per month by migraine severity (total; moderate or severe) in the OP efficacy analysis period, overall DBT mean, overall OL rimegepant mean, and in each month of the on-DBT and on-OL rimegepant efficacy analysis periods, number of days of MR efficacy data in these aforementioned periods, overall DBT mean, and overall OL rimegepant mean; MRM day values, changes and percent changes from OP in the aforementioned months, overall DBT mean, and overall OL rimegepant mean.

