#### **Reduction in MRM Days per Month in the DBT Phase**

The number of MRM days per month in the DBT phase will be examined relative to the number of MRM days per month in the OP for menstrual migraine evaluable mITT menstruating female subjects, i.e., mITT menstruating females with  $\geq 1$  day of eDiary MR efficacy data and  $\geq 14$  days of eDiary efficacy data (not necessarily consecutive) in both the OP analysis period and at least one month (i.e., 4-week interval) in the on-DBT efficacy analysis period (see Section 7.6.2).

Months in the DBT phase are defined in Section 6.3.1.2.

Analyses will be based on eDiary efficacy dates in the OP analysis period and on-DBT efficacy analysis period.

The number of MRM days per month will be prorated to 28 days, and derived as follows:

- OP:  $28 \times (\text{total number of MRM days in the OP analysis period}) / (\text{total number of efficacy data days in the OP analysis period})$ .
- Month (i.e., 4-week interval) in the on-DBT efficacy analysis period:  $28 \times (\text{total number of MRM days in the month}) / (\text{total number of efficacy data days in the month})$ . Subjects must have at least one day of MR efficacy data in the specified month to be evaluable.
- Overall DBT mean:  $28 \times (\text{total number of MRM days through Month 3 in the on-DBT efficacy analysis period}) / (\text{total number of efficacy data days through Month 3 in the on-DBT efficacy analysis period})$ .

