### Descriptive Analyses

Values and changes (both absolute and percent) from the OP in the number of MRM days per month in the OLE phase will be summarized descriptively as continuous parameters (including 2-sided normal 95% CIs for mean change) by as-randomized treatment group and overall and migraine severity (total; moderate or severe) in each month of the OLE phase and overall OL rimegepant mean.

Analyses are based on evaluable OL rimegepant mITT menstruating female subjects. In the percent change analyses, subjects must also have ≥ 1 MRM day of appropriate migraine severity in the OP analysis period to be included.

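### The OP line in the SAP's open-label MRM derivation points to the all-migraine-day formula, contradicting the MRM baseline that the same section names; programmed literally, it would create a spurious reduction.

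*SAP*

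**What the plan says.** SAP Section 6.3.3.1 handles MRM days separately for the double-blind treatment (DBT) phase and the open-label extension (OLE).

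- **DBT part.** The OP value is written out as a formula with numerator "total number of MRM days in the OP analysis period", divided by efficacy data days and scaled to 28. The treatment comparison uses OP MRM days as its covariate.
- **OLE part.** The opening sentence says that OLE MRM days "will be examined relative to the number of MRM days per month in the OP". The derivation list is introduced with "The number of MRM days per month will be prorated to 28 days and derived as follows". Its OP bullet then reads "OP: See Section 6.3.1.1".
- **Section 6.3.1.1.** This is the primary-endpoint section. Its only OP monthly formula has numerator "total number of migraine days in the OP analysis period", that is, migraine days of every kind.
- **OLE descriptive analyses.** They report "Values and changes (both absolute and percent) from the OP in the number of MRM days per month in the OLE phase", by severity (total; moderate or severe). Percent change requires at least one "MRM day of appropriate migraine severity in the OP analysis period to be included".

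The by-subject MRM listing described at the start of Section 6.3.3.1 also shows MRM days in the OP and MRM changes from OP.

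**The concern.** The OP bullet is an operative derivation line, and it leads to the wrong endpoint. A reference to a section with no usable formula would stop a programmer. This one leads to a complete formula with the same denominator and the same 28-day scaling, so it would run without error.

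The OLE MRM summary has no concurrent placebo group, because every subject in it takes rimegepant. Change from OP is the whole result, and no control arm would reveal a baseline on a different scale. If the bullet was programmed literally, each OLE MRM change and percent change would subtract an all-migraine-day count from an MRM count, which pushes the result towards apparent benefit.

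**Working it through.** The documents give no figure for this analysis, so there is none to reproduce. The check compares the two possible baselines.

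**Inputs from the documents**
- Menstrual interval: from "complete menstrual period start date – 2 days" to 2 days after the start, so 5 days per period (SAP 6.3.3.1).
- Eligibility: at least 6 migraine days and at most 18 headache days in the OP (Protocol 5.2).
- OP length: 28 days, plus up to 3 for scheduling (Protocol Table 1).

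**The two baselines**
- Literal: 28 × (all OP migraine days) / (OP efficacy data days).
- MRM: 28 × (OP MRM days) / (OP efficacy data days).

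**Bounds for total severity, literal baseline**
- Lowest OP value at 6 migraine days: 28 × 6/28 = 6.0, or 28 × 6/31 = 5.4 over 31 diary days.
- Highest OLE monthly MRM value with one period and a full diary: 28 × 5/28 = 5.0.
- Since 5.0 < 5.4, such a subject shows a reduction whatever the drug does.

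**Where the bound fails**
- Sparse diary: 5 MRM days give 28 × 5/24 = 5.8 at 24 diary days, but 28 × 5/23 = 6.1 at 23.
- Two periods in one 28-day month: up to 28 × 10/28 = 10.0.
- Moderate-or-severe analysis: the minimum of 6 counts migraine days of any severity, so it sets no floor here.
- Triptan or ergotamine days: Protocol Appendix 3 counts them as migraine days without limiting this to a phase. SAP 7.6.2.2, criterion 2b, counts them only in the on-DBT and on-OL periods. An eligible subject's OP value under the SAP could therefore fall below 6.

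**Expected change with no effect.** Assume one period, full diaries and no clustering of migraine around menstruation. A subject with b OP migraine days then expects 5b/28 MRM days per month, so the literal change is 5b/28 - b:

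| b | Expected MRM days | Literal change |
|---|---|---|
| 6 | 1.07 | -4.9 |
| 10 | 1.79 | -8.2 |
| 18 | 3.21 | -14.8 |

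The percent change is 100 × (5/28 - 1) = -82% for every b. With the MRM baseline the expected change is 0.

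**Simulation with no effect.** These assumptions are not in the documents: underlying migraine days uniform on 6 to 18, one menstrual interval in the OP, migraine risk inside the interval 1 to 3 times that outside, 0 to 40% of OLE diary days missing and at most 5% of OP days missing. Subjects needed at least 6 OP migraine days and 24 OP diary days. Ranges run over the scenarios.

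| OLE month | Baseline | Subjects with a reduction | Mean change (days) |
|---|---|---|---|
| One interval | Literal | 99.4% to 100% | -7.7 to -10.5 |
| Two intervals | Literal | 84% to 99.7% | -3.4 to -8.3 |
| One interval | MRM | 18% to 51% (15% to 50% increase) | -0.02 to -0.07 |

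In one further run, daily migraine risk in the OLE was 1.5 times that in the OP (risk ratio 2, 10% missing, one interval). The literal baseline still gave a mean change of -8.1 days, with 100% of subjects reduced after rounding. The MRM baseline gave +0.8.

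**The case against.** The strongest reply is that the SAP's intent is clear and only a pointer is wrong. The opening sentence, the sentence introducing the list, the descriptive analyses, the percent-change rule and the listing all name an MRM quantity in the OP, and the right formula stands in the same Section 6.3.3.1. The identical bullet appears in Section 6.3.1.2, for total migraine days in the OLE, where it is correct, so a copied line is a likely explanation, though the documents do not say so. Similar slips occur nearby: the DBT part cites Section 6.3.1.2 for its months, which Section 6.3.1.1 defines, and the missing-data list starts Months 10 to 13 after week 36 where Section 6.3.1.2 has week 48. A programmer might also notice OP values of 6 or more from a 5-day window, or a mismatch with the OP MRM values used in the DBT analysis.

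Most of this stands. A reader might infer that the SAP chose an all-migraine-day baseline, or that the reported OLE MRM result is falsely favourable. The documents support neither: they contradict themselves on the baseline and do not show what was programmed. A reader might also take 6 against 5 to mean that every subject must show a reduction; the exceptions above rule that out.

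The reply does not make the bullet correct. The percent-change rule decides who is included, not what is subtracted, so it would not catch the error. Version 10.0 of the SAP, issued after final database lock to correct errors, revised the MRM cohorts in this same section and left the line in place.

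**Conclusion.** The cross-reference is wrong, and the OLE part of Section 6.3.3.1 is internally inconsistent. This is a risk of misprogramming, conditional on the bullet having been followed literally. Under that condition, and for total severity, most subjects would show a reduction without any treatment effect. The simulated mean of about -8 to -10 days for one menstrual interval per month rests on the assumptions stated with it; the -8 in the two-subtraction example is only an illustration. For moderate-or-severe days the literal baseline also mixes endpoints, but the documents give no floor from which to bound the size.

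The reach is small. The affected summary is descriptive, with no model or p-value. It lies outside the hierarchy in SAP 6.1.2, and the MRM objective in SAP 1.2.3 covers the DBT phase only. The DBT MRM comparison uses the correct baseline and covariate. With the MRM baseline the artefact disappears.

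**What to change.** In the OLE part of SAP Section 6.3.3.1, replace the OP bullet with the explicit formula: 28 × (MRM days in the OP analysis period) / (efficacy data days in the OP analysis period), as in the DBT part of that section. Then confirm from the analysis programs which baseline was used for the Addendum Report.

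The text change is one line and needs no new data. If the all-migraine-day formula was programmed, rerun the OLE MRM changes and percent changes and check the MRM listing. If the MRM formula was used, a note recording the corrected reference is enough. The citation for the DBT months and the week range for Months 10 to 13 can be corrected in the same edit.

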### Missing MR Efficacy Data

Missing MR efficacy data in the OP and OLE phases will be assessed using the number and percentage of OL rimegepant mITT menstruating female subjects in the following categories:

- Evaluable
-

- Not evaluable, i.e., no days of MR efficacy data in the OP and no days of MR efficacy data in all 13 months (i.e., all 13 4-week intervals) of the OLE phase
  - No days of MR efficacy data in the OP
  - No days of MR efficacy data in any of the following months (i.e., 4-week intervals) of the OLE phase:
    - Months 1 to 3: > 12 to ≤ 24 weeks
    - Months 4 to 6: > 24 to ≤ 36 weeks
    - Months 7 to 9: > 36 to ≤ 48 weeks
    - Months 10 to 13: > 36 to ≤ 64 weeks

### Descriptive Analyses

Values and changes (both absolute and percent) from the OP in the number of MRM days per month in the OLE phase will be summarized descriptively as continuous parameters (including 2-sided normal 95% CIs for mean change) by as-randomized treatment group and overall and migraine severity (total; moderate or severe) in each month of the OLE phase and overall OL rimegepant mean.

Analyses are based on evaluable OL rimegepant mITT menstruating female subjects. In the percent change analyses, subjects must also have ≥ 1 MRM day of appropriate migraine severity in the OP analysis period to be included.

#### 6.3.3.2 *Reduction in Migraine Days in the First Week of the DBT Phase*

The number of migraine days in the first week of the DBT phase will be examined relative to the number of migraine days per week in the OP for evaluable first week mITT subjects, i.e., mITT subjects with at least one day of eDiary efficacy data in both the OP analysis period and the first week of the on-DBT analysis period.

The first week of the DBT phase is defined as study days 1 to 7. See Sections 7.4 and 7.5 for the definition of analysis periods and study days used to define analysis visit windows.

Analyses will be based on evaluable first week mITT subjects with eDiary efficacy dates in the OP analysis period and the on-DBT efficacy analysis period.

The number of migraine days per week will be prorated to 7 days, and derived as follows:

- OP:  $7 \times (\text{total number of migraine days in the OP analysis period}) / (\text{total number of efficacy data days in the OP analysis period})$ .
- First week of the on-DBT efficacy analysis period:  $7 \times (\text{total number of migraine days in the first week}) / (\text{total number of efficacy data days in the first week})$ . Subjects must have at least one day of efficacy data in the first week to be evaluable.

### Descriptive Analyses

---

Values and changes (both absolute and percent) from the OP in the number of migraine days per first week of the DBT phase will be summarized descriptively as continuous parameters (including 2-sided normal 95% CIs for mean change) by treatment group and migraine severity (total; moderate or severe).

In the percent change analyses, subjects must also have  $\geq 1$  migraine day of appropriate severity in the OP analysis period to be included.

### **Treatment Group Comparisons**

Analyses will be based on total severity, unless specified otherwise.

A generalized linear model will use the following variables: change from the OP in number of total migraine days per week in the first week as the dependent variable; number of total migraine days per week in the OP as a covariate; treatment group and prophylactic migraine medication use at randomization as fixed effects. The model will be repeated by prophylactic migraine medication use at randomization (yes, no). The following model estimates will be reported:

- LSM change from OP, SE, and 95% CI by randomization stratum (yes, no, overall) for each treatment group
- Difference in mean changes from OP between treatment groups (rimegepant – placebo), SE, 95% CI, and p-value by randomization stratum (yes, no)
- Difference in mean changes from OP between treatment groups (rimegepant – placebo), SE, 95% CI, and p-value. Results will support the exploratory objective.

These analyses will be repeated for moderate or severe migraine severity. All variables in the model will be the same, except (1) change from the OP in number of moderate or severe migraine days per week will be the dependent variable, and (2) number of moderate or severe migraine days per week in the OP will be the covariate.

#### **6.3.3.3 *Triptan or Ergotamine Days per Month***

This adhoc analysis was added to the CSR.

Triptan or ergotamine days are a subset of rescue medication days (see Section 6.3.2.2). Triptan or ergotamine days per month will be assessed as “Triptan or ergotamine days per 4 weeks” to correspond with the 4-week visit schedule. Triptan or ergotamine days per month are based on data from the previous visit to the current visit (i.e., 4-week interval) where a triptan or ergotamine day is defined as a day of efficacy data with complete reference time point date and a “yes” response to at least one of the following questions: taking triptan to treat headache or during aura; taking ergotamine to treat headache or during aura.

#### ***Triptan or Ergotamine Days per Month in the DBT Phase***

Analyses are based on evaluable mITT subjects with eDiary reference time point dates in the on-DBT efficacy analysis period.

The number of triptan or ergotamine days per month in the DBT phase will be prorated to 28 days and derived as follows:

- Month (i.e., 4-week interval) in the on-DBT efficacy analysis period:  $28 \times (\text{total number of triptan or ergotamine days in the month}) / (\text{total number of efficacy data days in the month})$ . Subjects must have  $\geq 14$  days of efficacy data (not necessarily consecutive) in the specified month to be evaluable.
- Overall DBT mean:  $28 \times (\text{total number of triptan or ergotamine days through Month 3 in the on-DBT efficacy analysis period}) / (\text{total number of efficacy data days through Month 3 in the on-DBT efficacy analysis period})$ .

### **Descriptive Analyses**

The number of triptan or ergotamine days per month in the DBT analysis period will be summarized descriptively as a continuous parameter (including 2-sided normal 95% CIs for mean) by treatment group in each month of the DBT phase and overall DBT mean.

### **Treatment Group Comparisons**

A generalized linear mixed effect model will have the following variables: number of triptan or ergotamine days per month as the dependent variable; subject as a random effect; treatment group, prophylactic migraine medication use at randomization, month (i.e., months 1 to 3 of the DBT phase), and the month-by-treatment group interaction as fixed effects. The model will be repeated by prophylactic migraine medication use at randomization (yes, no). The following model estimates will be reported:

- LSM, SE, and 95% CI by month and randomization stratum (yes, no, overall) for each treatment group
- Difference in LSMs between treatment groups (rimegepant – placebo), SE, 95% CI, and p-value by randomization stratum (yes, no) for each month
- Difference in LSMs between treatment groups (rimegepant – placebo), SE, 95% CI, and p-value for each month.
- Overall LSM, SE, and 95% CI by randomization stratum (yes, no, overall) for each treatment group
- Difference in overall LSMs between treatment groups (rimegepant – placebo), SE, 95% CI, and p-value by randomization stratum (yes, no)
- Difference in overall LSMs between treatment groups (rimegepant – placebo), SE, 95% CI, and p-value.

### **Triptan or Ergotamine Days per Month in the OLE Phase**

Analyses are based on evaluable OL rimegepant mITT subjects with eDiary reference time point dates in the on-OL rimegepant efficacy analysis period.

The number of triptan or ergotamine days per month in the OLE phase will be prorated to 28 days and derived as follows:

- Month (i.e., 4-week interval) in the on-OL rimegepant efficacy analysis period:  $28 \times (\text{total number of triptan or ergotamine days in the month}) / (\text{total number of efficacy data days in the month})$ . Subjects must have  $\geq 14$  days of efficacy data (not necessarily consecutive) in the specified month to be evaluable.
- Overall OL rimegepant mean:  $28 \times (\text{total number of triptan or ergotamine days through Month 13 in the on-OL rimegepant efficacy analysis period}) / (\text{total number of efficacy data days through Month 13 in the on-OL rimegepant efficacy analysis period})$ .

The number of triptan or ergotamine days per month in the OLE phase will be summarized descriptively as a continuous parameter (including 2-sided normal 95% CIs for mean) by treatment group and overall in each month of the OLE phase and overall OLE mean.

